Deferasirox (DFX, Exjade®) the second approved oral chelator, is a once-daily orally active iron chelator, firstly introduced in USA, and authorised in Europe under the Centralised Procedure for treating chronic iron overload due to frequent blood transfusions (≥ 7 ml/kg/month of packed red blood cells) in patients with beta thalassaemia major above 6 years of age and in patients under 6 years of age when DFO therapy is contraindicated. The safety and efficacy profile of DFX was compared with DFO, and non-inferiority to this drug was demonstrated in patients with LIC ≥ 7 mg Fe/g dw. Post marketing long-term data have identified renal impairment as a safety risk associated with DFX therapy in both paediatric and adult patients and consequently the SmPC has been updated accordingly (Annex 1). Nevertheless, DFX with its PK profile allowing the maintenance of plasma levels within the therapeutic range for 24-hour period, and permitting once-daily oral administration, is currently the most widely used chelator in the paediatric subset (Ceci A et al., 2011).

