6.3 Dose Adjustments

Dose adjustments for both DFP and DFX will be allowed for efficacy reasons (scaling up) or for safety reasons including the presence of markers indicative of over-chelation (scaling down).

DFP can be scaled up in steps of 12.5 mg/kg/day (to a maximum daily dose of 100 mg/kg) according to the individual patient's response defined as an increase of serum ferritin levels > 20% compared to the previous determination.

DFX will be scaled up in steps of 5 to 10 mg/kg (to a maximum daily dose of 40 mg/kg) according to the individual patient's response defined as an increase of ferritin levels > 20% compared to the previous determination.

For patients with a stable serum ferritin value >1500 (no increase or any increase <20%) and not showing a downtrend over a 3-month-period , DFP or DFX can be also increased.

DFP and DFX must be scaled down for the safety reasons detailed in **Table 4**.

Table 4. Scale down adjustment for DFP and DFX (safety reasons)

Serum creatinine increased by >33% from baseline OR Reduction in creatinine clearance (estimated with the Schwartz formula) ≤ 90ml/min and >60 ml/min in two consecutive measurements	No dose adjustment.	Reduce DFX in steps of 10 mg/kg/day until value returns to baseline value and continue DFX with the adjusted dose for 1 month. If the increase persists interrupt DFX. If after DFX interruption value returns to baseline value or > 90 ml/min for creatinine clearance restart DFX at 50% of the last dose and then escalate by 10 mg/kg/day at 1 month intervals provided that value increase does not recur. Monitor serum creatinine, creatinine clearance and urine protein/creatinine ratio weekly (+/- 7 days) during the period of abnormal value and during the first month after dose modification, then monthly.
Urine protein/creatinine ratio ≥ 0.5 in two consecutive measurements	No dose adjustment.	Reduce DFX in steps of 10 mg/kg/day until value returns to < 0.5. If the increase persists interrupt DFX. After the ratio improves, restart DFX at 50% of the last dose and then escalate by 10 mg/kg/day at 1 month intervals provided that value increase does not recur. Monitor serum creatinine, creatinine clearance and urine protein/creatinine ratio weekly (+/- 7 days) during the period of abnormal value and during the first month after dose modification, then monthly.

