ALT or AST > 10 ULN	Interrupt DFP. When levels return to < 5 ULN, restart DFP at 50% of the last dose and after 1 month scale it back up to the former dose.	Interrupt DFX. When levels return to < 5 ULN, restart DFX at 50% of the last dose and then escalate by 10 mg/kg/day at 1 month intervals provided that value increase does not recur.

CONFIDENTIAL

Severe skin rash	No dose adjustment.	Interrupt DFX . Once resolved, restart DFX at 50% of the last dose and then escalate by 5 mg/kg/day at two-weeks intervals.
Ferritin \leq 500 ng/ml	Reduce DFP to 50% of last dose. If ferritin is still <500 ng/ml at subsequent monthly evaluation, DFP may continue having consulted the Coordinating Investigator. When value returns > 500 ng/ml DFP can be scaled up to full dose.	Reduce DFX to 50% of last dose. If ferritin is still <500 ng/ml at subsequent monthly evaluation, DFX may continue having consulted the Coordinating Investigator. When value returns > 500 ng/ml restart DFX at 50% of the last dose and then escalate by 10 mg/kg/day at 1 month intervals.
Neutropenia(neutrophil count $<1500/\text{mm}^3$ and $\geq 1000/\text{mm}^3$ in two consecutive measurements)*	Interrupt DFP and monitor neutrophil count every 1-3 days or more frequently. When value returns $> 1500/\text{mm}^3$ for two consecutive measurements, and if deemed safe by the investigator, restart DFP at the last dose after having consulted the Coordinating Investigator.	Interrupt DFX and monitor neutrophil count every 1-3 days or more frequently. When value returns $> 1500/\text{mm}^3$ for two consecutive measurements, and if deemed safe by the investigator, restart DFX at the last dose after having consulted the Coordinating Investigator.
Moderate Neutropenia (neutrophil count $<1000/\text{mm}^3$ and $> 500/\text{mm}^3$) OR Severe Neutropenia/Agranulocytosis (neutrophil count $< 500/\text{mm}^3$) Infection	Interrupt DFP. Exit from the protocol.	Interrupt DFX. Exit from the protocol.

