11.7 Safety evaluation

The assessment of safety will be based mainly on the frequency of AEs and on the number of laboratory values that fall outside of pre-determined ranges. Other safety data (e.g. ECG, vital signs, and special tests) will be considered as appropriate.

AEs will be summarized by presenting, for each treatment, the number and percentage of patients having any AE and having an AE in each body system. Any other information collected (e.g. severity or relatedness to study medication) will be listed as appropriate.

Laboratory data will be summarized by presenting shift tables using extended normal ranges (baseline to most extreme post-baseline value), by presenting summary statistics of raw data and change from baseline values (means, medians, standard deviations, ranges) and by the flagging of notable values in data listings.

Data from other tests (e.g. ECG or vital signs) will be listed, notable values will be flagged, and any other information collected will be listed as appropriate. If suitable summary statistics will be presented. Any statistical tests performed to explore the data will be used only to highlight any interesting comparisons that may warrant further consideration. Further details will be specified in the analysis plan provided prior to data base lock.

A summary of clinically relevant toxic events, i.e., adverse events that are serious, adverse events or laboratory tests that lead to change of dose of study medication or discontinuation from study medication will be provided.

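### Section 11.7 admits non-serious toxic events by dose action, which Table 4 orders for renal findings and severe rash under DFX but not under DFP

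*Combined protocol and SAP*

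**What the plan says.** The last paragraph of Section 11.7 (Safety evaluation) promises a summary of toxic events judged clinically relevant. Serious events form one group in it, and the second group is defined by action on treatment: "adverse events or laboratory tests that lead to change of dose of study medication or discontinuation from study medication will be provided". A non-serious adverse event or laboratory abnormality thus qualifies only if treatment was changed or stopped.

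Whether treatment is changed is set by Section 6.3: "DFP and DFX must be scaled down for the safety reasons detailed in" Table 4. Three rows of that table treat the drugs differently:

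- For the trigger "Serum creatinine increased by >33% from baseline OR Reduction in creatinine clearance" (the row goes on to give clearance limits), the DFP cell reads "No dose adjustment". The DFX cell orders stepwise reduction, then interruption if the change persists.
- For a urine protein/creatinine ratio of 0.5 or more in two consecutive measurements, the DFP cell again orders no adjustment. The DFX cell says "Reduce DFX in steps of 10 mg/kg/day until value returns to < 0.5", with interruption if it persists.
- For severe skin rash, the DFP cell orders no adjustment. DFX is interrupted: "Once resolved, restart DFX at 50% of the last dose and then escalate by 5 mg/kg/day at two-weeks intervals".

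The column headings of Table 4 did not survive in the text available, but the drug named in the cells makes the assignment clear. Section 3.1 states of the comparator: "Post marketing long-term data have identified renal impairment as a safety risk associated with DFX therapy".

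**The concern.** A toxicity count that compares two arms should depend on what happened to the patient. Here it depends partly on a management step that the protocol itself sets differently by arm. Two patients with the same confirmed proteinuria, neither case serious and neither patient stopping treatment, are classified differently because of the drug assigned.

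This is the only planned summary that carries the label of clinically relevant toxicity, and safety and tolerability is a secondary objective (Section 2.2). Two of the three affected rows concern the kidney, the organ for which the protocol names a DFX risk. A reader who compares the two columns would see an excess under DFX even if the true rates were equal, and the error favours the experimental drug.

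**Working it through.** **Step 1: set Table 4 against the Section 11.7 definition.** For an event that is not serious and does not end treatment, with Table 4 followed:

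| Table 4 trigger | DFP action | DFX action | Counted in the summary |
|---|---|---|---|
| Creatinine rise or reduced clearance | none | reduce, interrupt if persistent | DFX only |
| Urine protein/creatinine ratio ≥0.5, twice | none | reduce, interrupt if persistent | DFX only |
| Severe skin rash | none | interrupt | DFX only |
| ALT or AST >10 ULN | interrupt | interrupt | both |
| Ferritin ≤500 ng/mL | reduce | reduce | both |
| Mild neutropenia | interrupt | interrupt | both |
| Arthralgia | interrupt | interrupt | both |

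Moderate and severe neutropenia mean exit in both arms and so count in both. The nausea row is broken in the text available and is not judged. The asymmetry is confined to three rows.

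**Step 2: can the event enter by another route?** A severe rash is not automatically serious, since Section 16.3 separates severity from seriousness. Serious events and discontinuations count in both arms. The discontinuation route is itself slightly uneven: Section 9 item 3 (prolonged low-dose treatment for safety reasons) names DFX only.

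**Step 3: do the other summaries give the same comparison evenly?** Only in part.
- Shift tables use extended normal ranges. Section 5.2 excludes patients with creatinine above the upper limit for age, so a rise of more than 33% can stay within range and show no shift.
- Change-from-baseline summaries give means, medians, standard deviations and ranges, not the number of patients past a trigger.
- Adverse events are tabulated by body system. Severity is listed as appropriate, so no planned table compares severe rash by arm.
- A laboratory abnormality is an adverse event only if the investigator judges it clinically significant (Section 16.1), and the trial is open label (Section 6.5).

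**Step 4: size.** The plan gives no figure for this summary and no event rates. The arm size follows from Section 11.12: 310 / (1 − 0.20) = 387.5, rounded up to 388, or 194 per arm.

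Let r be the true risk of one of these findings, equal in both arms, and s the share of them that are serious or end treatment. Both are assumptions.

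- Expected DFX count = 194 × r
- Expected DFP count = 194 × r × s
- Spurious difference in proportions = r × (1 − s)

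| r | s | DFX | DFP | Difference (points) |
|---|---|---|---|---|
| 2% | 0 | 3.9 | 0 | 2.0 |
| 5% | 0 | 9.7 | 0 | 5.0 |
| 5% | 0.25 | 9.7 | 2.4 | 3.8 |
| 10% | 0 | 19.4 | 0 | 10.0 |
| 10% | 0.25 | 19.4 | 4.9 | 7.5 |
| 10% | 0.5 | 19.4 | 9.7 | 5.0 |
| 20% | 0.5 | 38.8 | 19.4 | 10.0 |

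For example, with r = 10% and s = 0.25: 194 × 0.10 = 19.4, 194 × 0.10 × 0.25 = 4.85, and 0.10 × 0.75 = 7.5 points. A definition by finding, applied alike in both arms, has an expected difference of 0 in every row.

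**The case against.** The strongest reply is that Section 11.7 rests the safety assessment mainly on adverse event frequency and on counts of laboratory values outside pre-determined ranges. Neither depends on dose action. The summary at issue is one descriptive item, with no planned test. Section 11.5 lists safety dose changes with their cause, so a reader can trace which DFX entries come from the DFX-only rows. Counting events that led to dose change is also a legitimate measure of tolerability. And neutropenia, the harm the protocol attributes to DFP in Section 8, prompts action in both arms and is notified by the serious-event procedure whatever its severity (Section 16.6), so the summary does not shield it.

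All of this stands, and it limits the point. A reader might infer that the plan hides renal signals under DFP. It does not: they remain in the shift tables, change-from-baseline summaries, flagged listings and out-of-range counts. Nor can it be said that those counts ignore the Table 4 thresholds, because Section 11.7 does not state the ranges and defers details to an analysis plan before database lock. A reader might also infer that the DFP count must be zero. It need not be: important medical events may be judged serious (Section 16.1), Section 9 item 5 applies to both arms, and Section 7.3.2 leaves the clinician free to depart from protocol treatment.

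What the reply does not remove is the unequal entry rule. A tolerability count presented as clinically relevant toxicity, with no note that the dose rules differ, invites a comparison it cannot support.

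**Conclusion.** The point holds for one descriptive summary, three rows of Table 4, and non-serious events that do not end treatment. Within those limits the counting rule produces a difference in favour of DFP when the true risks are equal. The size is r × (1 − s): for example 5 to 10 points at 5% to 10% risk with s = 0, or 7.5 points at 10% risk with s = 0.25. It rests on assumed rates, an assumed equal risk and adherence to Table 4.

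The counts above should not be turned into significance tests. Any p-value would only restate the assumed rates and the near-zero DFP count, for a comparison the plan does not test. The documents do not support a claim that the safety evaluation as a whole is biased or that data are lost. The primary efficacy analysis is unaffected.

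**What to change.** Change Section 11.7, or the analysis plan it defers to before database lock, as follows.

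1. Define the toxic-event summary by the observed finding, identically in both arms whatever was done with the dose: the Table 4 trigger values and severe rash, plus serious adverse events and discontinuations. Show each component on its own line, because Section 9 item 3 can end treatment under DFX only.
2. Derive the renal and proteinuria triggers from the common scheduled visits only (V3 as baseline, then V4 to V15). Table 4 places extra weekly renal monitoring in the DFX cells alone, so a count over all samples would raise detection under DFX. Where two consecutive measurements are required, use consecutive scheduled visits. Show single-visit exceedances beside the confirmed ones, since a DFX dose reduction between visits may prevent confirmation.
3. Report the number and percentage of patients per arm, with a descriptive risk difference and 95% confidence interval.
4. Keep events leading to dose change or discontinuation as a separate tolerability table, with a footnote that the dose rules differ by arm.

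No dose rule is to be changed, and no view is taken on the rules. The cost is revised wording and one extra table. Sections 7.3.15 and 7.3.16 already schedule the renal and urine measurements at these visits in both arms, and adverse events are recorded in both. The downside for the sponsor is that the DFP count may look less favourable.

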11.8 Pharmacokinetic evaluation

The objective of the pharmacokinetic analysis is to evaluate the influence of potential covariates (e.g., subject's demographics, disease status and concomitant medications) on the parameters of interest.

The data collected in this study will be enriched with data obtained during the DEEP-1 DFP pharmacokinetic study. Covariate effects will be assessed using non-linear mixed effects modelling. During each step in the covariate model building process, statistical diagnostic tools will be used to evaluate model performance.

11.9 Exploratory PKPD analysis

The main objective of this analysis is to explore whether a correlation can be established between treatment response and steady-state concentrations of the investigational drugs. Therefore, pharmacokinetic data collected for DFP and DFX will be analysed in conjunction with the primary pharmacodynamic endpoints (ferritin and MRI). Data will subsequently be modelled using nonlinear mixed effects modelling, as implemented in the software NONMEM ([name], USA).

11.10 Health Care Resources Utilisation

The level of resource utilization in each treatment group will be summarized but will not be subjected to inferential statistics.

11.11 Interim analyses

No interim analyses are planned for this study. Two times a year a safety update will be provided to an independent Data Safety Monitoring Committee (DSMC), reviewing, evaluating and categorizing safety findings in the context of the entire program of paediatric registration trials for DFP.

11.12 Sample Size and power considerations

Primary efficacy objective

Assuming type I and type II errors of 0.025 and 0.20, respectively, and a one-sided test, and under the assumptions that the expected proportion of subjects declared treatment successes in the DFX arm is 65%, and the expected proportion of subjects declared treatment successes in the DFP arm is 67.5% a sample size of 310 subjects, randomized in a 1:1 ratio to DFP or DPX will yield 80% power to demonstrate non-inferiority of DFP versus DFX. Taking into account a possible dropout rate of about 20% a total enrolment of 388 patients aged from 1 month to less than 18 years are expected to be included in the trial.

Secondary efficacy objective

Sample size requirements for the secondary efficacy objectives (non-inferiority in terms of ferritin levels and cardiac MRI T2*) are provided in the following.

Based on published literature, testing for non-inferiority is appropriate also when comparing DFP to DFX efficacy in terms of serum ferritin levels. In this case, considering a hypothesis testing on the continuous measure, a non inferiority margin of 400 ng/ml is considered a reliable estimate of the true allowed maximum difference between the IMPs in order to assume DFP to be non-inferior to DFX in controlling iron overload in patients affected by hereditary haemoglobinopathies. The standard deviation of the differences is available by pooling findings from paediatric studies conducted in Europe and outside (El Alfay M et al., 2010), and a reliable and conservative estimate can be 1000 ng/mL.

On these assumptions, 310 evaluable patients are sufficient to provide at least 90% power to demonstrate non inferiority of DFP to DFX, assuming a type I error of 0.025 and a one-sided test.

When considering efficacy in terms of cardiac MRI T2*, less reliable estimates of treatment efficacy are available, especially in the paediatric population. However, there are no reasons for not assuming at least a non inferiority of DFP to DFX, considering also the known beneficial effects of DFP at the cardiac level. Based on the limited published figures of cardiac MRI T2* in the paediatric population and taking into account adult data, some plausible scenarios of sample sizes and related powers are provided in the following **Table 7**, assuming a type I error of 0.025 and a one-sided test. Detailed power curves will be provided in the statistical plan.

Table 7. Sample size and power on cardiac MRI T2* (percentage of successfully chelated patients)

DFX/DFP Success (%)	65/70	65/70	70/75	70/75
Non inferiority margin (%)	-12.5	-10	-12.5	-10
Power (%)	80	75	80	75
n (per group)	112	135	102	123

On these calculations, a test for non inferiority in terms of percentage of successfully chelated patients according to the criterion 4.3.2 as defined in Section 4.3 Primary endpoint is considered feasible and supported by an adequate power whenever cardiac MRI T2* is available in about 60-70% of the evaluable population.

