The choice of this composite endpoint allows the feasibility of the trial in the entire paediatric population and provides an up to date approach to the evaluation of the global iron accumulation in paediatric transfusion-dependent patients. In addition the use of a composite endpoint (rather than an alternative one) allows avoiding multiplicity while adequately characterising (total body iron load and in the heart) the beneficial effect of treatments.

Each component of the composite endpoint will be considered for secondary analyses with the intent to clarify the interpretation of the composite. For such analyses no adjustment for multiplicity will be foreseen (see **Section 11.2**).

Based on the above defined composite endpoint, non inferiority is established if the lower limit of two sided 95% confidence interval of the difference in success rate is above - 12.5%. The choice of this margin is based on clinical considerations starting from the available evidences for the effects of DFP and DFX on ferritin levels and cardiac iron load.

In details, the percentage of expected success for DFX and DFP measured as change from baseline to 1 year treatment is summarised in the following **Table 6**:

Table 6: Success rates for DFP and DFX

Serum ferritin levels	76% (95%CI: 63.6-88.5) DFP mean dose 66.4 mg/kg/day (Addis A et al, 1999) Paediatric population included in the meta-analysis but not analysed separately.	57% (95%CI: 50.7-63.3) DFX used at 20-30 mg/kg/day (Taher A et al, 2009) 75 adult and 162 paediatric patients
Cardiac MRI T2*	66% Higher percentage in splenectomised patients (Pennell DJ et al, 2006) 29 adults	69.5% in patients with moderate-to-mild baseline cardiac iron load (≥ 10 to <20 ms) DFX mean dose 33.1 \pm 3.7 mg/kg/day (Pennell DJ et al, 2010) 72 adult and 29 paediatric patients

Pooling together these findings, the expected percentage of success in the composite endpoint is assumed to be equal to 65% and 67.5% for DFX and DFP, respectively. The non inferiority margin of 12.5% has been considered to be a good estimate of an achievable lower bound of the true difference between the DFP and DFX.

Other secondary objectives include the evaluation of treatment efficacy in terms of liver iron concentration, the assessment of treatment safety and tolerability profiles, healthcare resources utilisation and patient global assessment and the analysis of the relationship of the demographic covariates and the disposition of DFP.

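### Table 7's 75–80% power for cardiac T2* non-inferiority holds only if deferiprone (DFP) is truly 5 points better than deferasirox (DFX), an advantage for which the plan gives no figure

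*Combined protocol and SAP*

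**What the plan says.** Section 11.6 plans descriptive statistics for cardiac T2*. It adds a formal non-inferiority test on T2* success (criterion B of section 4.3.1) if scans are available in at least 60–70% of the evaluable population.

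Section 11.12 supports that test with Table 7. It concedes that T2* efficacy estimates are less reliable, especially in children, but holds that "there are no reasons for not assuming at least a non inferiority of DFP to DFX", pointing to known cardiac benefits of DFP. The scenarios are computed "assuming a type I error of 0.025 and a one-sided test. Detailed power curves will be provided in the statistical plan". The rows of Table 7 are:

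- "DFX/DFP Success (%) 65/70 65/70 70/75 70/75"
- "Non inferiority margin (%) -12.5 -10 -12.5 -10"
- "Power (%) 80 75 80 75"
- "n (per group) 112 135 102 123"

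The text after the table concludes that the test is feasible and adequately powered once T2* is available in about 60–70% of evaluable patients.

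Table 6 in section 11.1 lists the success rates the plan expects after one year. For cardiac T2* the DFX entry is "69.5% in patients with moderate-to-mild baseline cardiac iron load", from 72 adults and 29 children. The DFP entry is 66%, from 29 adults.

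**The concern.** Every column of Table 7 gives DFP a 5-point advantage. No column has equal rates or a DFP deficit. Yet the plan's only T2* figures put DFP 3.5 points below DFX (66 − 69.5), and the text does not explain the departure. Assuming that DFP is at least non-inferior is a weaker statement than assuming it is 5 points better, and only the second produces the tabulated power.

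In a non-inferiority test, an assumed advantage adds directly to the margin. With a margin of 12.5 points and an advantage of 5, the distance that drives power is 17.5 points, not 12.5. If the advantage is absent, power falls sharply at the same n. A reader who takes the adequate-power statement at face value could then give too much weight to a T2* interval that fails to exclude the margin.

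**Working it through.** **Inputs.** One-sided type I error 0.025, 1:1 allocation, and the rates, margins and n per group of Table 7 (section 11.12). T2* expectations are from Table 6 (section 11.1). The +2.5-point case borrows the primary endpoint's assumption of 65% for DFX and 67.5% for DFP (section 11.12). The T2* test method is not spelled out, so I assume the unpooled normal approximation that section 11.6 gives for the primary endpoint.

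**Formula.** With margin M, n per group and v = pDFP(1 − pDFP) + pDFX(1 − pDFX):

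Power = Φ( (pDFP − pDFX + M) / √(v/n) − 1.96 )

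**Step 1: reproduce Table 7.** For 65/70, M = 0.125, n = 112:

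- v = 0.65×0.35 + 0.70×0.30 = 0.4375
- √(0.4375/112) = 0.0625
- 0.175/0.0625 = 2.80
- Φ(2.80 − 1.96) = 80.0%

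The other three columns give 75.0%, 80.1% and 75.1%. Solving for n gives 112.1, 135.0, 101.9 and 122.6 against the stated 112, 135, 102 and 123. Table 7 reproduces.

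**Step 2: change only the assumed rates.** For the first column (M = 0.125, n = 112):

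- DFP +2.5 points (65/67.5): v = 0.4469, SE = 0.0632, 0.150/0.0632 = 2.37, power 66.1%
- Equal rates (65/65): v = 0.4550, SE = 0.0637, 0.125/0.0637 = 1.96, power 50.1%
- Table 6 rates (DFX 69.5, DFP 66): v = 0.4364, SE = 0.0624, 0.090/0.0624 = 1.44, power 30.2%

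All four columns, keeping each column's n and margin. The +2.5 and equal-rate rows keep that column's DFX rate:

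| True DFP − DFX | M 12.5, n 112 | M 10, n 135 | M 12.5, n 102 | M 10, n 123 |
|---|---|---|---|---|
| +5 (as in Table 7) | 80.0% | 75.0% | 80.1% | 75.1% |
| +2.5 | 66.1% | 58.4% | 65.8% | 58.2% |
| 0 | 50.1% | 40.6% | 49.5% | 40.2% |
| −3.5 (Table 6 rates) | 30.2% | 20.7% | 28.0% | 19.3% |

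A simulation of the Wald interval on the Table 6 rates (400,000 trials per column) gives 30.7%, 20.9%, 28.0% and 19.1%.

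**Step 3: how firm is the Table 6 difference?** Taking the quoted patient counts as denominators (an assumption: 29 for DFP, 72 + 29 = 101 for DFX):

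- SE = √(0.66×0.34/29 + 0.695×0.305/101) = 0.099
- 95% interval = −0.035 ± 1.96×0.099, or about −23 to +16 points

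This interval includes zero and includes +5.

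**Step 4: primary endpoint.** At 65/67.5, M = 0.125 and 155 per arm, power is 79.8%, in line with the stated 80%. The primary sample size is not in question here.

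**The case against.** The best defence is that Table 7 is correct for the assumptions it displays, that section 11.12 admits the estimates are less reliable and calls the scenarios only plausible, and that it gives a reason for favouring DFP. It also defers detailed power curves to a statistical plan, and such curves normally span a range of true differences. The test is secondary and conditional on scan availability, and section 11.6 relies on descriptive T2* statistics to support the efficacy conclusions.

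Much of this stands. There is no arithmetic error, and the consequence is limited to a secondary analysis. Three parts do not settle the matter. The cardiac benefit that the background section (3.1) documents is against deferoxamine, while sections 4 and 11.1 say no study compares DFP with DFX directly. Uncertain rates call for scenarios on both sides of zero, not only favourable ones. The promised curves name no less favourable case, and they leave the adequate-power sentence as it is.

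Two stronger readings are tempting, and the documents support neither:

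- **That DFP is expected to be worse on T2*, so true power is 19–30%.** Table 6 sets 29 adults beside a DFX group restricted to baseline T2* of 10 to under 20 ms. The trial also enrols patients at or above 20 ms, for whom criterion B uses a different success rule. The interval in step 3 is compatible with a DFP advantage, so 19–30% is a sensitivity result and not a forecast.
- **That power is at most about 50% unless DFP is a full 5 points better.** Power moves continuously with the true difference. At +2.5 points it is already 58–66%.

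**Conclusion.** The concern holds as a matter of unstated dependence, not of miscalculation. Power of 75–80% requires a true 5-point DFP advantage on T2* success, and the plan supplies no figure for it. At the same n and margins, power is 58–66% at +2.5 points, 40–50% at equal rates and 19–30% on the plan's own Table 6 rates.

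The conclusion does not rest on trusting Table 6, because the neutral equal-rates case alone brings power to 50% or below. It does rest on the T2* test using the same normal-approximation interval as the primary analysis, and on the n per group in Table 7 being reached. The unconditional statement that power is adequate should be corrected.

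**What to change.** In section 11.12:

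1. Add columns to Table 7 for a +2.5-point DFP advantage, for equal rates and for the Table 6 rates, the last labelled as a sensitivity case from small, non-comparable sources.
2. State that 75–80% power requires a true 5-point DFP advantage.
3. Replace the adequate-power conclusion after Table 7 with the conditional figures.
4. State, there or with the T2* analysis in section 11.6, that failing to exclude the margin on T2* is not evidence of cardiac inferiority.

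The cost is a wording change in the statistical sections and a less favourable power statement. No extra patients are needed, and the primary sample size stays as it is.
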